9.3 Level of Significance

There is no formal hypothesis test planned for this study. A statistically significant level of 0.05 is used for calculation of CI.

9.4 Interim Analysis

No formal interim analysis is planned. However, the safety, PK and efficacy data will be regularly reviewed and monitored for decisions involving dose escalation in Phase 1 and continuation in Phase 2 of the study.

9.5 Statistical Analyses

9.5.1 Safety Analyses

The safety assessments include adverse events, laboratory tests (hematology, clinical chemistry, coagulation, and urinalysis), ECG, physical examination, vital signs, ECOG performance status, and medical history. All the safety data in the SAS will be summarized and listed by phase, treatment group, and cohort.

9.5.1.1 Adverse Events

A treatment-emergent adverse event (TEAE) is any AE either reported for the first time or worsening of a pre-existing event after the first dose of study drug. Analysis of AEs will be limited to TEAEs, but data listings will include all AEs regardless of their timing to study drug administration. Adverse events will be tabulated by the MedDRA preferred term and system organ class. Severity of AEs will be based on the NCI CTCAE v5.0 using Grades 1 through 4.

The subset of AEs considered by the investigator to have a relationship to study drug will be considered to be treatment-related AEs. If the investigator does not specify the relationship of the AE to study drug, then the AE will be considered treatment-related. The incidence, frequency, duration, and severity of all AEs (regardless of causality) will be tabulated.

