h During Cycle 1 subjects will be required to stay at the study site for safety observation for 4 hours post end of infusion. At Cycle 1, vital signs (blood pressure, pulse, respiratory rate, and body temperature) will be collected pre-dose, at end of infusion (+10 minutes), and every 60 minutes (\pm 10 minutes) thereafter. On Day 1 of all subsequent cycles, subjects will be required to be observed for a minimum of 1 hour post end of infusion or per PI discretion if indicated. After cycle 1, vital signs (blood pressure, pulse, respiratory rate, and body temperature) will be assessed pre-dose and at end of infusion (+10 minutes). Subjects will also be assessed for the onset of acute AEs.

i All 12-lead ECGs will be performed with the subject in a recumbent or semirecumbent position after 5 minutes of rest and should not be performed within 15 minutes after a blood collection.

j A single 12-lead ECG should be performed anytime at Screening and EOT.

k ECGs will be performed on Day 1 of Cycles 1 and 5, in conjunction with PK samples at the following timepoints: pre-infusion and post-infusion (+30 minutes). Additional ECGs should be performed per PI discretion if any clinically significant abnormal findings are noted or as indicated.

l AEs will be collected after ICF has been signed and through end of study. The severity of AEs will be assessed using NCI CTCAE v5.0 Grades 1 through 4. The NCI CTCAE v5.0 severity of Grade 5 will not be used;

m If a central line is used for study drug infusion, collect blood samples via peripheral blood draw to prevent sample contamination.

n Visit/lab assessments on Day 2 and 3 are required for Phase 1 subjects only.

o For Phase 1a, tumor biopsies are optional. Biopsies are required for all Phase 1b and Phase 2 subjects. Biopsies will be collected at Pre-Screening (Phase 1b and Phase 2 only), Screening (Phase 1 subjects), and at Cycle 3 (prior to Cycle 4 dose). An optional EOT biopsy will be collected for subjects who consent for EOT biopsy at time of ICF.

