6.4 Follow-up

6.4.1 Safety Follow-up

The safety follow-up period is the interval between the EOT visit and the scheduled follow-ups, which should occur 30 days (+ 7 days) and 90 days (+ 7 days) after the EOT visit (or after the last dose of study drug if the EOT visit was not performed). AEs and SAEs must be reported up until at least 90 days after the last dose of study drug, the date of the last follow-up, or until toxicities resolve, return to baseline, or are deemed irreversible, whichever is longer. The safety follow-up must be performed before any new systemic anticancer therapy is started regardless of whether it occurs before the end of the 30- or 90-day safety follow-up period; it can, in fact, be done on the same day provided it is done before the start of the new systemic anticancer therapy (e.g. prior to dosing).

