7.4 Poststudy Anticancer Therapy Status

The investigator or qualified designee will review all new systemic anticancer therapy initiated after the last dose of study drug. If a subject initiates a new systemic anticancer therapy within 30 to 90 days after the last dose of study drug, the 30-day or 90-day safety follow-up should occur before the first dose of the new systemic anticancer therapy.

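### The TEAE window in Section 9.5.1.1 has no end, so AEs reported after a subject starts another anticancer therapy enter the all-causality tables for the primary safety endpoint

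*Combined protocol and SAP*

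**What the plan says.** Section 2.2.1 makes the frequency, duration and severity of AEs the primary safety endpoint. Section 9.5.1.1 decides which events are analysed. It says that "A treatment-emergent adverse event (TEAE) is any AE either reported for the first time or worsening of a pre-existing event after the first dose of" NC762. The section then states: "Analysis of AEs will be limited to TEAEs, but data listings will include all AEs regardless of their timing to study drug administration". On causality it says "The incidence, frequency, duration, and severity of all AEs (regardless of causality) will be tabulated", and for a blank assessment "If the investigator does not specify the relationship of the AE to study drug, then the AE will be considered treatment-related".

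The end of AE collection is described in four places:

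- Section 6.4.1: "AEs and SAEs must be reported up until at least 90 days after the last dose of study drug", or to the last follow-up, or to resolution, whichever of these comes last.
- Section 8.1.2: the same 90-day minimum for new AEs.
- Table 7, footnote l: "AEs will be collected after ICF has been signed and through end of study".
- Section 8.1.1: an AE can occur up to the end of the follow-up period, with no length given.

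New treatment is provided for in Section 7.4: "If a subject initiates a new systemic anticancer therapy within 30 to 90 days after the last dose of study drug", the safety follow-up is to come before its first dose. Section 6.4.1 and Table 7 footnote b say the same. None of the three says that AE reporting then ends.

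**The concern.** The TEAE definition has a start and no stop, and no collection rule supplies the stop. A subject who leaves NC762 and begins chemotherapy or another immunotherapy on day 30 after the last dose is still inside the 90-day reporting minimum. Toxicity of the new drug that is reported then is an event first seen after the first NC762 dose, so it meets the definition and is tabulated.

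The study has no control arm against which such events could be set. The all-causality TEAE rates would describe NC762 together with whatever came next.

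The protocol does deal with new therapy elsewhere. Section 9.5.3 censors PFS and DoR at the use of another anticancer drug. Imaging stops at new systemic therapy (Sections 6.4.2 and 7.6.1.1.2). Section 8.5 has a separate pregnancy-reporting limit for subjects who start it. The AE analysis has no matching rule.

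**Working it through.** No sample size, power or error rate in the plan depends on the TEAE window, so there is no planned figure to reproduce. The check has a textual part and an illustrative part.

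**1. Does any rule close the window?**

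| Place | End stated | Stops at new therapy? |
|---|---|---|
| 9.5.1.1 (TEAE) | none | no |
| 6.4.1 | at least 90 days after last dose, or later | no; only the visit is moved |
| 8.1.2 | at least 90 days after last dose | no |
| Table 7, footnote l | end of study | no |
| 8.1.1 | end of an undefined follow-up period | not stated |

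Only Section 8.1.1 could be read as closing early, and it conflicts with the 90-day minimum and with footnote l.

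**2. Which results are exposed?**

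- DLT and MTD decisions use the 28 days from Cycle 1 Day 1 (Section 5.4.2). Not exposed.
- The MNTD rule counts Grade 3 or higher toxicity related to study drug (Table 3). Partly protected by causality.
- Treatment-related tables: partly protected. Under Appendix 2 an event with a clearly more likely alternative cause is not related, but a blank assessment counts as related (9.5.1.1).
- All-causality TEAE tables: fully exposed.

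**3. Time inside the window on another drug, for one subject who starts it**

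Let s be the days from last NC762 dose to new therapy (assumed). Days of the 90-day minimum spent on the new therapy = 90 − s.

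- s = 14: 76 days, 76/90 = 84%
- s = 30: 60 days, 60/90 = 67%
- s = 60: 30 days, 30/90 = 33%

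If first to last dose spans 84 days (assumed), the window is 84 + 90 = 174 days and the shares are 76/174 = 44%, 60/174 = 34% and 30/174 = 17%. With a 42-day span (132 days) they are 76/132 = 58%, 60/132 = 45% and 30/132 = 23%.

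**4. Effect on a tabulated incidence**

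Let b be the AE incidence before any new therapy, f the share of subjects who start new therapy inside the window, and g the chance that such a subject has that kind of AE reported on it. Treating these as independent:

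observed incidence = b + (1 − b) × f × g

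All three are assumptions. With b = 20%:

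- f = 30%, g = 20%: 0.20 + 0.80 × 0.30 × 0.20 = 24.8%
- f = 70%, g = 40%: 0.20 + 0.80 × 0.70 × 0.40 = 42.4%

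In a full Phase 2 cohort of 24 (Section 9.2.2) this is 24 × 0.248 = 6.0 to 24 × 0.424 = 10.2 subjects, against 24 × 0.20 = 4.8 with a window closed at new therapy. With b = 30% the same inputs give 34.2% to 49.6%. If few later AEs are reported, g is small and the excess, (1 − b) × f × g, shrinks towards zero.

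**The case against.** The strongest reply is that the window closes in practice. Section 6.4.1 describes the safety follow-up period as running from the EOT visit to the scheduled follow-ups. Those follow-ups must precede any new systemic therapy, and Section 8.1.1 limits AEs to the follow-up period. Read together, these could mean that AE capture ends when the visit is brought forward. Part of this stands: Table 7 schedules no safety visit after new therapy begins, so reports from then on would be largely unsolicited. It does not settle the matter, because the 90-day minimum and footnote l remain and the visit rule does not override them. Two analysts could build different TEAE tables from the same text.

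Section 9 defers further detail to an SAP, which might set an end date. Nothing in the document supplied does so.

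A reader might infer more than the documents support:

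- *That dose decisions are compromised.* DLT and MTD decisions rest on 28 days, and the MNTD rule on related toxicity. The protocol does let AEs from any time on study be considered for dose, schedule and MNTD (Section 3.1.2), but that is a judgement and not a count.
- *That a third or a half of the safety data is foreign.* The shares in step 3 are calendar time for one assumed subject. The planned tables are not rates per unit time.
- *That most subjects will start new therapy in the window.* Section 7.4 is conditional, and entrants have progressed on, cannot tolerate or refuse standard treatment (Section 4.1). The proportion is unknown. Starting 14 days after a day-42 dose would mean starting on the day of the nominal Week 8 scan, whereas stable subjects may stay on NC762 until a confirmatory scan 4 to 6 weeks later.
- *That cohorts would differ by speed of progression and not by dose.* Nothing in the documents shows this.
- *That efficacy is uniformly cut at new therapy.* PFS and DoR are; OS is not.

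**Conclusion.** The point holds for the all-causality TEAE tables. As written, Section 9.5.1.1 counts any AE reported after a subject moves to another anticancer therapy, for as long as AEs are collected. This is a stated rule with an unintended consequence, in the analysis of the primary safety endpoint, and it should be changed.

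Its size is unknown. It depends on how many subjects start new therapy inside the window and how many of their later AEs are reported. The 24.8% to 42.4% against 20% is an illustration of how the mechanism scales, not an estimate for this trial, and the brought-forward safety visit pushes the effect towards the lower end or below it.

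**What to change.** In Section 9.5.1.1, define a TEAE as an AE that starts or worsens from the first dose to the earlier of (a) 90 days after the last dose or (b) the day before new systemic anticancer therapy, plus any later AE that the investigator actively assesses as related to NC762. Placing late related events inside the definition keeps it consistent with the rule that AE analysis is limited to TEAEs. A blank causality field should not by itself bring a later event in. List all other later AEs separately.

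Also:

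- Reconcile the end of AE collection across Sections 6.4.1, 8.1.1, 8.1.2 and Table 7 footnote l.
- Confirm that the eCRF captures the start date of new therapy. Table 7 asks about post-study therapy at EOT and both safety visits, but those visits are meant to precede it, so the date may be missed.

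The cost is wording plus that eCRF check. The new definition does not itself require sites to report differently. The downside should be stated in the plan: late events judged unrelated, whether after new therapy or after day 90 without it, move from the TEAE tables to the listing. Sections 5.4.7 and 8.8 note that irAEs can appear several months after the last dose, so a delayed irAE wrongly attributed to something else could be among them.

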9.5.1.2 Vital Signs

Descriptive statistics and mean change from baseline will be determined for vital signs (blood pressure, pulse, respiratory rate, and body temperature) at each assessment time. Vital sign results will be reviewed for clinically notable abnormalities (see Table 15) and subjects exhibiting clinically notable vital sign abnormalities will be listed. A value will be considered an "alert" value if it is outside the established range and shows a > 25% change from baseline.

Table 15: Criteria for Clinically Notable Vital Sign Abnormalities

Parameter	High Threshold	Low Threshold
Systolic blood pressure	> 155 mmHg	< 85 mmHg
Diastolic blood pressure	> 100 mmHg	< 40 mmHg
Pulse	> 100 bpm	< 45 bpm
Temperature	> 38°C	< 35.5°C
Respiratory rate	> 24 breaths/min	< 8 breaths/min

9.5.1.3 Electrocardiograms

Descriptive statistics and mean change from baseline will be determined for each ECG parameter at each assessment time. ECG results will be reviewed for clinically notable abnormalities according to predefined criteria (see Table 16). Subjects exhibiting clinically notable ECG abnormalities will be listed.

Table 16: Criteria for Clinically Notable Electrocardiogram Abnormalities

Parameter	High Threshold	Low Threshold
QTcF	> 460 msec	< 295 msec
PR	> 220 msec	< 75 msec
QRS	> 120 msec	< 50 msec
QT	> 500 msec	< 300 msec
RR	> 1330 msec	< 600 msec

QTcF = Fridericia correction.

9.5.2 PK Analyses

The PK analyses will be based off the PAS, and PK time-concentration data will be summarized, listed, and plotted. PK parameters (AUC_{0-336} , $AUC_{0-\infty}$, C_{max} , $t_{1/2}$, etc.) derived from time-concentration data will be summarized.

9.5.3 Efficacy Analyses

The response will be assessed by CT/MRI image during screening and every 8 weeks (56 \pm 7 days) post-dosing for 6 months and then every 12 weeks (84 \pm 7 days) thereafter. The efficacy study endpoints include ORR, DCR, DoR, PFS, and OS. Tumor response will be determined according to RECIST v1.1. Time-to-event data (DoR, PFS, and OS) will be analyzed using the Kaplan-Meier method. All the efficacy data will be summarized by phase, dose group, and cohort.

- ORR includes RECIST v1.1 complete and partial response (CR or PR). ORR with 95% exact confidence interval (CI) will be summarized by phase, dose group, and cohort.
- DCR includes RECIST v1.1 complete, partial response, and stable disease (CR, PR or stable disease lasting 24 weeks or longer). DCR with 95% exact CI will be summarized by phase, dose group, and cohort.
- DoR is defined as the duration from the first documented ORR to the first documented progressive disease or death due to any cause, whichever occurs first. For subjects who are alive and progression-free at the time of discontinuation from study, data cutoff for analysis, or use of other anticancer drug, DoR will be censored at the last tumor assessment date.

The DoR will only be analyzed for the subgroup of subjects with an objective response.

DoR = (progressive disease, death, or censored date) – (date of first response + 1)

- PFS is defined as from starting study treatment to the first documented progressive disease or death due to any cause, whichever occurs first. For subjects who are alive and progression-free at the time of discontinuation from study, data cutoff for analysis, or use of other anticancer drug, PFS will be censored at the last tumor assessment date.

PFS = (progressive disease, death, or censored date) – (date of first dose of study drug + 1)

- OS is defined as from starting study treatment to death due to any cause. For subjects who are alive will be censored at the date of last known alive (LKA).

OS = (Death or LKA date) – (date of first dose of study drug + 1)

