5.5.2 Withdrawal Procedures

If the decision is made to permanently discontinue the study drug, the subject will be withdrawn from the study, and the end-of-treatment (EOT) visit should be conducted. Reasonable efforts should be made to have the subject complete the follow-up visits. These visits are described in [Section 6.4](#). The last date of the last dose of study drug and the reason for subject withdrawal will be recorded in the eCRF.

If a subject is withdrawn from the study:

- The study site monitor and medical monitor must be notified.
- The reason(s) for withdrawal must be documented in the subject's medical record and in the eCRF
- The EOT visit should be performed
- The date of the EOT visit should be recorded in the eCRF
- Subjects must be followed for safety until the time of the follow-up visit or until study drug-related toxicities resolve, return to baseline, or are deemed irreversible, whichever is longest

If the subject discontinues study drug and actively withdraws consent for collection of follow-up data (safety follow-up or disease assessment), then no additional data collection should occur; however, subjects will have the option of withdrawing consent for study drug but continuing in the follow-up period of the study for safety/efficacy assessments.

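### Section 9.5.3 subtracts (start date + 1) in the DoR, PFS and OS formulas, so every duration is one day short of elapsed time and a same-day event gives -1

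*Combined protocol and SAP*

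**What the plan says.** Section 9.5.3 (Efficacy Analyses) gives three formulas. In each, the closing bracket comes directly after the 1:

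- "DoR = (progressive disease, death, or censored date) – (date of first response + 1"
- "PFS = (progressive disease, death, or censored date) – (date of first dose of study drug + 1"
- "OS = (Death or LKA date) – (date of first dose of study drug + 1"

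The same section also defines PFS in words: "PFS is defined as from starting study treatment to the first documented progressive disease or death due to any cause, whichever occurs first". OS likewise runs from the start of treatment, and DoR from the first documented response. All three are analyzed by Kaplan-Meier.

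For a subject alive and progression-free at study discontinuation, data cutoff or use of another anticancer drug, "PFS will be censored at the last tumor assessment date". DoR is censored in the same way. On assessments, the section says "The response will be assessed by CT/MRI image during screening and every 8 weeks" and "Tumor response will be determined according to RECIST v1.1".

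Section 7.6.1.1.1 allows the baseline scan up to 30 days before first dose. Section 7.6.1.1.2 places the first imaging assessment at 8 weeks. The opening of Section 9 leaves additional analysis detail to a SAP.

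**The concern.** The formulas do not compute what the definitions describe. A time measured from the start of treatment is either the elapsed difference or the inclusive count that calls the first day Day 1. The printed expression is neither. The form is identical in all three formulas, so a programmer who follows the text will apply it throughout, and a same-day end date returns a negative duration. Software or a data check may drop or reject negative times, and dropping them would change the risk set.

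The second matter is separate, and moving the bracket does not cure it. The only PFS censoring date is the last tumor assessment, with no restriction to post-baseline scans and no fallback. The FAS (Section 9.1) requires one full dose but no post-baseline scan, so a subject without one stays in the PFS analysis and needs a date.

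**Working it through.** **Inputs.** The three formulas and the censoring rule come from Section 9.5.3, the 30-day limit on the baseline scan from 7.6.1.1.1, and the first scan at 56 ± 7 days from 7.6.1.1.2 and 9.5.3. The plan works no example of a duration, so there is no figure of its own to reproduce.

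**Algebra.** As printed: end - (start + 1) = (end - start) - 1. Elapsed: end - start. Inclusive: (end - start) + 1. The printed form is therefore always 1 below elapsed and 2 below inclusive.

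**Dates.** Take an illustrative first dose on 1 September 2021 (an assumption; the differences do not depend on it).

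| End date | Days after first dose | As printed | Elapsed | Inclusive |
|---|---|---|---|---|
| 1 Sep 2021 | 0 | -1 | 0 | 1 |
| 2 Sep 2021 | 1 | 0 | 1 | 2 |
| 20 Oct 2021 | 49 | 48 | 49 | 50 |
| 27 Oct 2021 | 56 | 55 | 56 | 57 |
| 3 Nov 2021 | 63 | 62 | 63 | 64 |
| 16 Feb 2022 | 168 | 167 | 168 | 169 |

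**Relative size.** Across the first scan window the shortfall against elapsed time is 1/63 = 1.6% to 1/49 = 2.0%. Against the inclusive count it is 2/64 = 3.1% to 2/50 = 4.0%. At 168 days it is 1/168 = 0.6% and 2/169 = 1.2%.

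**DoR.** If the response scan is also the last assessment, DoR is -1 as printed (0 elapsed, 1 inclusive). If the last assessment is 28 days after first response, it is 27 as printed (28 elapsed, 29 inclusive).

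**Kaplan-Meier.** Take twelve illustrative subjects with elapsed times 0, 49, 54, 56, 58, 60, 63, 110, 112, 115 (censored), 168 and 170 (censored). The step heights are identical under all three counts. Survival reaches 6/12 = 0.5 at the sixth event, so the median, taken as the first time survival is 0.5 or less, is 59 as printed, 60 elapsed and 61 inclusive. If a program dropped the -1 record (an assumption), 11 subjects would remain. Survival would be 6/11 = 0.55 after the fifth event and 5/11 = 0.45 after the sixth, and the as-printed median would be 63 - 1 = 62.

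**Subject without a post-baseline scan.** Two readings of the last tumor assessment are open:

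- If it includes the screening scan, as 9.5.3's reference to assessment during screening permits, the censoring date precedes time zero. For a scan 1 day before first dose, PFS is -2 as printed. At the 30-day limit it is -31 as printed, and still -30 (elapsed) or -29 (inclusive) with the bracket corrected.
- If it follows 7.6.1.1.2, where imaging assessments begin at 8 weeks, no censoring date exists.

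Censoring at first dose would give 0 (elapsed) or 1 (inclusive), but -1 under the printed formula. The bracket therefore has to be corrected as well.

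**The case against.** Several objections have force.

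*It is an evident slip.* Probably so, but the intended count is an inference. Elapsed and inclusive times both fit the definitions in words, so the text does not tell a programmer which to use.

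*The SAP will settle it.* Section 9 does defer detail to a SAP, and a fallback censoring rule is the kind of detail that belongs there. The secondary point can therefore say only that the rule is absent from the available text. The deferral does not rescue the formulas, which are printed in the protocol and would have to be contradicted.

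*Negative times will hardly occur.* For PFS and OS this largely stands. A death on the day of first dose enters the FAS only if a full dose was given, so such events should be rare.

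A reader might also infer that any responder with no later scan gets a DoR of -1. The documents support that only if an unconfirmed response counts. Section 9.5.3 uses RECIST v1.1 and states no confirmation rule. However, Section 7.6.1 makes modified RECIST the primary response measure, Section 2.2.2 names both criteria, and 7.6.1.1.2 asks for confirmation at least 4 weeks later under modified RECIST. A confirmed responder's DoR is then at least 28 - 1 = 27 as printed.

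A reader might further infer that the 4-week waiver of the discontinuation scan, new therapy, or any withdrawal is enough to leave a subject without a post-baseline scan. That goes too far. After the waiver, Section 7.6.1.1.3 still asks for imaging every 8 weeks. New therapy ends imaging, but leaves the gap only if the discontinuation scan was waived or missed. Under Section 5.5.2, collection stops only for a subject who "actively withdraws consent for collection of follow-up data (safety follow-up or disease assessment), then no additional data collection should occur"; a subject may leave study drug and stay in follow-up.

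**Conclusion.** The point holds, and it is minor. As written, all three formulas give (end - start) - 1 day, which contradicts the section's own definitions and yields -1 for a same-day end date. For DoR, the -1 arises only if an unconfirmed response counts and the response scan is the last assessment.

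A reader might infer that the survival estimates would be distorted. They would not be, provided negative times are retained: the shift is constant, the order of times and the step heights are unchanged, and medians move by 1 to 2 days. DoR, PFS and OS are secondary (Section 2.2.2), Section 9.3 plans no formal hypothesis test, and the Phase 2 stage 1 rule uses responses, so sample size and continuation decisions are untouched.

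The secondary gap is real but narrow. It can arise at a data cutoff before the week-8 scan, after active withdrawal of consent for follow-up data, or when new therapy starts and the discontinuation scan was waived or missed. The figure of -31 is a worst case, needing a scan at the 30-day limit and the literal reading of the censoring rule. Confidence is high for the formulas. For the missing rule, the conclusion is limited to the text available.

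**What to change.** Choose one convention and use it in all three formulas: either end date - start date + 1 (move the + 1 outside the bracket) or end date - start date. The start date is first dose for PFS and OS, and first response for DoR. Either convention fits the definitions; the choice is the sponsor's.

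Add one sentence to the PFS rule, or confirm that the SAP already has it: subjects who are alive and progression-free with no post-baseline tumor assessment are censored for PFS at the date of first dose (Day 1).

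Keep one matter out of this change. Section 5.6.3 counts palliative radiation as clinical progression for PFS, while 9.5.3 refers to documented progressive disease. That needs its own reconciliation.

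The cost is wording in the protocol and SAP and a few lines of programming, best done before the analysis programs are written. No data collection, visit or sample size changes.
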